Hyperglycemia is common during TH as lower temperatures decrease insulin secretion and increase insulin resistance. Many patients with heart failure and cardiogenic shock have concomitant diabetes and glucose control can often be difficult to achieve in these critically ill patients. Clinically significant hyperglycemia will be defined as glucose level exceeding 200mg/d requiring continuous insulin infusion in patients without a diagnosis of diabetes mellitus. Hyperglycemia in patients with diagnosis of diabetes mellitus, or hyperglycemia as a result of other identifiable causes (i.e. administration of steroids, adrenal derangements) will not be considered as a result of TH. In patients who develop hyperglycemia requiring continuous insulin infusion as a direct result of TH, the patient will be treated expectantly and hyperglycemia will be recorded as an adverse event. During TH period, blood glucose will be measured at least hourly during TH, especially in patients receiving intravenous insulin, and during rewarming, when glucose levels can fall.

Hypothermia will lower serum potassium levels, primarily by promoting inward cellular potassium flux, although hypothermia also induces a mild diuresis with concurrent electrolyte wasting. Serum electrolytes will be measured at regular intervals (every 4–6 hours). Potassium will be repleted to maintain levels above 3.5 mEq/L. Rewarming reverses the potassium flux and increases serum levels, so repletion will be held 4 hours before rewarming begins. Clinically significant hyperkalemia is unusual in patients with preserved renal function. In patients with hypokalemia not due to other identifiable causes (diuretic administration, adrenal derangements, etc.), potassium supplements will be administered as per standard of care. Hypokalemia with potassium levels below 3.0mEq/L not secondary to other identifiable causes in patients undergoing TH will be considered an adverse event.

The target temperature of 32-34°C will be achieved using the intravascular cooling catheters. The body temperature will be recorded every 1-2 hours as per the CCU policy in the TH group (as well as the control group). The time spent in the therapeutic window will be recorded and reported. Any deviations outside of the range, specifically $<32^{\circ}\text{C}$ lasting >5 minutes will be reported as an adverse event.

Mitigating Risks associated with cooling catheter insertion:

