Serious Adverse Event (SAE) Ref: ISO 14155-2011 Ref: MEDDEV 2.7/3 12/2010	
Adverse event that:
 
• Led to death,• Led to serious deterioration in the health of the subject, that either resulted in:
○ a life-threatening illness or injury, or○ a permanent impairment of a body structure or a body function, or

Table A – Safety Reporting Definitions

Term	Definition
	
○ in-patient or prolonged hospitalization of existing hospitalization, or○ medical or surgical intervention to prevent life-threatening illness or injury or permanent impairment to a body structure or a body function● Led to fetal distress, fetal death, or a congenital abnormality or birth defect. 
NOTE: Planned hospitalization for a pre-existing condition, or a procedure required by the clinical investigational plan, without serious deterioration in health, is not considered a serious adverse event.

Serious Adverse Device Effect (SADE) Ref: ISO 14155-2011 Ref: MEDDEV 2.7/3 12/2010	Adverse device effect that has resulted in any of the consequences characteristic of a serious adverse event.
Unanticipated Adverse Device Effect (UADE) Ref: 21 CFR Part 812	Any serious adverse effect on health or safety or any life-threatening problem or death caused by, or associated with, a device, if that effect, problem, or death was not previously identified in nature, severity, or degree of incidence in the investigational plan or application (including a supplementary plan or application), or any other unanticipated serious problem associated with a device that relates to the rights, safety, or welfare of subjects.
Device Deficiency Ref: ISO 14155-2011 Ref: MEDDEV 2.7/3 12/2010	
A device deficiency is any inadequacy of a medical device with respect to its identity, quality, durability, reliability, safety or performance.
 
NOTE: Device deficiencies include malfunctions, misuse or use errors, and inadequate labeling.

Abbreviations: EC=Ethics Committee; IRB=Institutional Review Board

Underlying diseases are not reported as AEs unless there is an increase in severity or frequency during the course of the investigation.

Relationship to Study Device(s) and Reporting Requirements

The Investigator will assess the relationship of the AE to the study device as related or unrelated.

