Table B – Criteria for Assessing Relationship of Study Device to Adverse Event

Classification	Description
Unrelated	The adverse event is determined to be due to a concurrent illness or effect of another device/drug and is not related to the investigational product.
Related	
• The adverse event is determined to be potentially related to the investigational product, and an alternative etiology is equally or less likely compared to the potential relationship to investigational product, or• There is a strong relationship to investigational product, or recurs on re-challenge, and another etiology is unlikely, or• There is no other reasonable medical explanation for the event.

Table C – Adverse Event Reporting

Event Classification	Event Recording	Communication to FDA	Communication to IRB
Adverse Event	
• Event reviewed and classified by PI• Event recorded in Oncore Adverse event database	Detail of all AE's will be given at time of annual report.	Details provided at time of annual review, per IRB policy.
Serious Adverse Event including Serious Adverse Device Effects	
• Event reviewed and classified by PI• Event recorded in Oncore Adverse event database	Reported via From 3500 within 48 hours of PI knowledge.	Details provided at time of annual review, per IRB policy (as these are not unanticipated events).
Unanticipated Adverse Device Effect / Unanticipated Serious Adverse Device Effect	
• Event reviewed and classified by PIStudy will be halted if event presents a significant or unreasonable risk to subjects enrolled in the study• Event recorded	Reported as soon as possible, but within 48 hours of PI knowledge, via From 3500.	UADE reported within 10 days of PI knowledge USADE reported directly to IRB Chairman upon PI knowledge, followed by formal reporting to the IRB within 48 hours. Study will be halted if event presents a

Table C – Adverse Event Reporting

Event Classification	Event Recording	Communication to FDA	Communication to IRB
	in Oncore Adverse event database		significant or unreasonable risk to subjects enrolled in the study

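### The protocol rules out TH-attributed hyperglycemia in every patient with diagnosed diabetes, which conflicts with the charter's event-by-event relatedness rule

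*Combined protocol and SAP*

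**What the plan says.** The hyperglycemia paragraph under Mitigating Risks associated with TH does four things.

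- It gives a mechanism: "Hyperglycemia is common during TH as lower temperatures decrease insulin secretion and increase insulin resistance".
- It describes the population: "Many patients with heart failure and cardiogenic shock have concomitant diabetes", and it notes that glucose is often hard to control in these critically ill patients.
- It defines the event: "Clinically significant hyperglycemia will be defined as glucose level exceeding 200mg/d requiring continuous insulin infusion in patients without a diagnosis of diabetes mellitus".
- It fixes attribution: "Hyperglycemia in patients with diagnosis of diabetes mellitus, or hyperglycemia as a result of other identifiable causes", with steroids and adrenal disorders as examples of such causes, "will not be considered as a result of TH".

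Its one recording instruction begins "In patients who develop hyperglycemia requiring continuous insulin infusion as a direct result of TH" and says that such a case is recorded as an adverse event.

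The DSMB charter (Appendix 2, section 5) takes a different route. After Table A it states: "Underlying diseases are not reported as AEs unless there is an increase in severity or frequency during the course of the investigation". Table B classes an event as related when, among other routes, it is potentially related and "an alternative etiology is equally or less likely compared to the potential relationship to investigational product". Section D of the protocol (Data Safety Monitoring Board) and section 2 of the charter give the DSMB final adjudication of all adverse events.

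**The concern.** The trial is a pilot whose stated purpose is the safety and tolerability of TH, and hyperglycemia is on its list of anticipated TH risks. A rule that settles causality from a baseline diagnosis removes a whole group from the TH-attributed count of that risk before any event is looked at.

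Two hypothetical patients show the effect. Patient A has no diabetes, reaches 210 mg/dL during cooling and starts an insulin infusion; this can be a TH event. Patient B has diabetes treated with tablets, goes from 150 mg/dL before cooling to 420 mg/dL during it, and also starts an infusion; this cannot be a TH event. Table B would put patient B to a case-by-case judgment, and cooling could well be found at least as likely a cause as the diabetes.

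At stake is what the DSMB and the planners of a later trial can learn about glucose under TH in patients with diabetes. A low TH-attributed count could be read as tolerance when part of it is produced by the definition.

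**Working it through.** **Step 1: set the rules side by side.**

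| Question | Hyperglycemia paragraph | General rules |
|---|---|---|
| Can a patient with diabetes meet the event definition? | No | Yes: Table A covers any untoward occurrence, including abnormal laboratory findings |
| Is worsened diabetes recorded as an adverse event? | Silent; it instructs recording only for a direct result of TH | Yes, if severity or frequency increases (charter, after Table A) |
| Can it be related to TH? | No, fixed in advance | Yes, judged per event (Table B) |
| Who decides in the end? | The rule itself | The DSMB (protocol section D, charter section 2) |

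Rows 3 and 4 conflict. Row 2 is a tension: staff can satisfy both texts by recording the event and classing it as unrelated, but the hyperglycemia paragraph does not tell them to, so two coordinators could handle the same patient differently.

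**Step 2: is there a figure to reproduce?** No. The plan states no hyperglycemia rate, diabetic share or event risk. Hyperglycemia is not among the primary or secondary endpoints, and Statistical Methods names no analysis of it.

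**Step 3: illustrate the size.** From the plan: 10 TH patients (Target Enrollment and Study Duration). Assumed: diabetic share d from 20% to 50%; event risk rN = 20% without diabetes; event risk rD = 20% or 40% with diabetes.

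- Rate if every patient could count = rN(1 − d) + rD·d
- TH-attributed rate over all 10 under the rule = rN(1 − d)
- Zero events in n patients: one-sided 95% upper bound = 1 − 0.05^(1/n)

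| d | Patients who can count | Rate, rD = 20% | Rate, rD = 40% | Rate under the rule | Upper bound at zero events, patients who can count |
|---|---|---|---|---|---|
| 20% | 8 | 20% | 24% | 16% | 31.2% |
| 30% | 7 | 20% | 26% | 14% | 34.8% |
| 40% | 6 | 20% | 28% | 12% | 39.3% |
| 50% | 5 | 20% | 30% | 10% | 45.1% |

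Example at d = 40%, rD = 40%: 0.20 × 0.60 + 0.40 × 0.40 = 0.28, against 0.20 × 0.60 = 0.12. If all 10 could count, the bound at zero events would be 1 − 0.05^(1/10) = 25.9%.

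**Step 4: does the loss always reach the diabetic share?** No. With rN = 20%, rD = 10% and d = 40%, the full rate is 0.12 + 0.04 = 0.16 and the share lost is 0.04/0.16 = 25%, below 40%.

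**The case against.** The strongest reply is that the paragraph governs attribution and not reporting. It never says that hyperglycemia in patients with diabetes goes unrecorded. Section D collects treatment-emergent events whether or not they are thought related, Table A defines an adverse event without regard to relatedness, and the DSMB is to receive the details of all adverse events. This stands. A reader might infer that the charter's sentence on underlying disease is flatly contradicted, or that the DSMB will learn nothing about patients with diabetes; the documents support neither. What remains is that the TH-attributed label is barred. The notices that section D spells out cover expected events that end the protocol and unexpected events. Hyperglycemia is expected and is not said to end cooling, so it reaches the DSMB only if someone first records it.

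A second reply is that this is an ordinary attribution convention: bradycardia that needs pacing is not counted against cooling when conduction disease was already present. That is fair as far as it goes. But ventricular arrhythmias that need intervention are all recorded and their cause is judged afterwards, and hypokalemia is excluded only for an identified cause. The protocol is not uniform, and for hyperglycemia its own mechanism argues against a blanket exclusion.

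A third reply is that the numbers are assumptions and small: 20% against 10% to 16% of 10 patients is 2 expected events against 1 to 1.6. That also stands, and the table above should be read in that light.

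**Conclusion.** The point holds as a defect in safety attribution. For any patient with diagnosed diabetes, hyperglycemia due to TH is impossible by rule, and that conflicts with Table B and with final adjudication by the DSMB. It is in tension with, but does not strictly contradict, the charter's rule on worsened underlying disease.

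The only certain quantity is the zero. The fall from 20% to between 16% and 10% rests on an assumed equal risk and an assumed diabetic share of 20% to 50%.

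Three stronger readings are tempting and should not be drawn:

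- That a planned hyperglycemia rate is biased. No rate or denominator is planned, and no endpoint is touched.
- That the understatement is at least the diabetic share. This needs the risk in patients with diabetes to be no lower than in the others.
- That patients with diabetes are a proven high-risk group for TH-induced hyperglycemia. The protocol says that control is difficult, not that this event is more frequent in them.

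The wording should still be changed, because the trial exists to describe safety and the repair is small.

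**What to change.** Reconcile the hyperglycemia paragraph with section 5 of the charter:

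1. Remove the restriction to patients without diabetes from the event definition, and delete the statement that excludes attribution to TH in patients with diabetes.
2. Record, in both arms and regardless of diabetes status, hyperglycemia above the existing glucose threshold that leads to a new continuous insulin infusion after randomization.
3. Assign relatedness under Table B, with final adjudication by the DSMB.
4. List events by arm and baseline diabetes status with denominators, as counts without tests. Under the assumed shares, a 10-patient arm has only 2 to 5 patients with diabetes.

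This changes what is recorded, not how anyone is treated. Medical history and medications are already collected at baseline. The costs are these. More events will be recorded, some of them background diabetes. The start of an insulin infusion after randomization needs its own case report form item, because the schedule provides only for vasoactive dosing. And because Appendix 1 schedules hourly glucose checks only for cooled patients, more events may be found in the TH arm simply because it is watched more closely. The comparison between arms must therefore be reported as descriptive with unequal ascertainment, and it cannot by itself separate background diabetes from an effect of TH.

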1. TTE
2. Hemodynamics
3. Metabolic parameters
4. Physiologic parameters and vital signs (including temperature)
5. Electrocardiogram
6. Blood sample for future research

Parameters collected during cooling protocol (18-24 hours after onset of cooling, prior to rewarming):

1. Hemodynamics
2. Metabolic parameters
3. Physiologic parameters and vital signs (body temperature measurements every 1-2 hours, as per the CCU policy)
4. Electrocardiogram

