administration of medications or a dialysis catheter for temporary dialysis. After successful insertion of the cooling catheter, it will be connected to the Thermogard XP® thermal regulation system. The Quattro® catheter functions as both a central venous triple lumen catheter as well as a cooling catheter. Cooling is achieved by circulating normal saline in a closed system through the catheter. The flow and temperature (range 4°C to 42°C) of the circulating saline serves as the heat exchange mechanism and is controlled by the external Thermoguard® thermal regulation system. The temperature is measured and adjustments are made by the thermal regulation system to automatically maintain target temperature. The target temperature is achieved within 2-3 hours of initiation of TH. Rewarming is accomplished using the same balloon catheter system and heat exchange occurs without infusion of any saline or fluids into the patient. In clinical trials, intravenous catheter based cooling system has been shown to achieve target temperature faster and maintain target temperature with more precision.^{12,14,15}

Medical therapy in both intervention and non-intervention groups will be based on the current recommendations for management of cardiogenic shock. This includes inotropic therapy (i.e. dobutamine or milrinone) for cardiac support, vasopressor therapy (i.e. norepinephrine, dopamine, phenylephrine, epinephrine) to achieve target blood pressure (mean arterial blood pressure \geq 60 mmHg), diuretics for volume removal, and mechanical circulatory support as clinically indicated. All patients included in this study will have pulmonary artery (PA) catheters inserted within 12 hours of randomization via either the internal jugular or femoral venous approach to monitor real-time hemodynamics. The clinicians in the CCU will use the data from PA catheters (cardiac output, mixed venous saturation, systemic vascular resistance, etc.) to guide therapy for both the intervention and non-intervention groups. The primary investigator of this study ([name]) will have no role in the clinical management of the patients.

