The risks associated with insertion of a cooling catheter are the same as insertion of any central lumen catheter. These include, but are not limited to, bleeding, infection, and vascular injury. Previously published studies have quoted risk of localized hematomas at 4.7% and risk of vascular injury (most frequently due to inadvertent arterial puncture) at $<1\%$.²³ Incidence of line-associated blood stream infection has been reported as 80-189 episodes per 100,000 patient years.²³

Insertion of a central venous catheter is standard of care in patients in cardiogenic shock to allow for administration of inotropes/vasopressors. The ZOLL Quattro catheters include three standard

central venous catheter infusion lumens to allow for administration of these vasoactive medications. Therefore, patients randomized to TH arm will not need an additional central venous line. Rather, insertion of a cooling catheter will serve the purpose of initiation and maintenance of TH while also allowing for administration of drugs via the infusion lumens. The risk associated with cooling catheter insertion is not expected to be higher than insertion of a standard central venous line.

C. Monitoring of Safety:

During the intervention period, participants will be monitored by physicians, nurses, and technicians in accordance with standard medical care. This includes 24-hour monitored telemetry, with measurement of heart rate, blood pressure, oxygen saturation, and respiratory rate. Real-time hemodynamic monitoring will be measured using pulmonary artery catheters. Blood glucose and electrolyte measurements will be performed as per protocol for patients undergoing therapeutic hypothermia, and correction of abnormalities will be performed by the treating team. Shivering will be monitored by the treating nurse, per ICU protocol, and will be reported to the treating team. TH will not influence the clinician's medical decisions – any medical or mechanical intervention necessary based on clinical status will be allowed.

D. Data Safety Monitoring Board:

Adverse events will be reviewed by the Data Safety Monitoring Board as described below. The study will be halted upon the discovery of unanticipated adverse device events that present a significant or unreasonable risk to subjects enrolled in the study.

The DSMB will meet (in person or via telephone conference) a minimum of 3 times:

- after treatment of the first 4 subjects (2 in the TH arm and 2 in the control arm)

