Appendix 1 – Schedule of Study Activities

	Baseline	18-24 hours (after randomization)	48-96 hours (after randomization)	30-day Follow-Up	90-day Follow-Up
Informed Consent	X				
Review Medial History	X				
Review Medication History	X				
Height and Weight	X				
Vital Signs ^a	X	X	X		
Echocardiogram (TTE)	X	X	X		
Electrocardiogram (ECG)	X	X	X		
Hemodynamics ^b	X	X	X		
Blood Tests ^c	X	X	X		
Vasoactive Medication Dosing		X			
Potassium (pts randomized to cooling)		Q 4 hours			
Glucose Checks (pts randomized to cooling)		Q 1 hour			
Urine Output	X	X	X		
Randomization	X				
Adverse Events		X	X	X ^d	X ^d

^a blood pressure, heart rate, temperature (bladder or esophageal), respiratory rate

^b RA pressures, RV pressures, PA pressures, pulmonary capillary wedge pressure (PCWP), Fick cardiac output and cardiac index, systemic vascular resistance (SVR), pulmonary vascular resistance (PVR), cardiac power and cardiac power index, mixed venous saturation (MVO2)

^c serum lactate level, basic metabolic panel, hepatic function, coagulation parameters, complete blood count (CBC), arterial blood gas (ABG), and optional blood samples for future research

^d to be completed in clinic, when possible, or by phone

^e items to be charged to research during cooling include: meperidine

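### The below-32°C adverse event has a 5-minute criterion, but the only temperature record the protocol specifies during cooling is one reading every 1-2 hours

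*Combined protocol and SAP*

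**What the plan says.** Under Mitigating Risks associated with TH, one short paragraph of the protocol contains three statements about temperature:

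- The recording rule: "The body temperature will be recorded every 1-2 hours as per the CCU policy in the TH group (as well as the control group".
- The adverse event: a deviation out of range, specifically below 32°C, "lasting >5 minutes will be reported as an adverse event".
- A summary measure: "The time spent in the therapeutic window will be recorded and reported".

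Methods, C. Timing of Data Collection, repeats the interval for the cooling period: "body temperature measurements every 1-2 hours, as per the CCU policy". No other section gives a recording frequency during cooling.

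The Procedures section describes a finer signal at the bedside: "The temperature is measured and adjustments are made by the thermal regulation system to automatically maintain target temperature". It also names the core probe site. It does not say that these readings are stored, exported, alarmed or used to identify the adverse event.

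Appendix 1 lists temperature as a vital sign at the scheduled assessments. It has separate cooling-arm rows for potassium and for glucose ("Glucose Checks (pts randomized to cooling"), but none for temperature.

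**The concern.** The event is defined by a duration in minutes, while the stated record has gaps of 60 to 120 minutes. Hypokalemia, in the same section, is defined by a level, so a single scheduled sample can establish it. A duration criterion cannot be established that way.

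The Objective section says this pilot is meant to establish the safety of therapeutic hypothermia, and the protocol itself chose overcooling as a reportable event. With about 10 cooled patients, readers and the DSMB would be interpreting a count that may be zero or one. If that count comes from the charted readings, it reflects the charting interval as well as how well temperature was controlled. Under D. Data Safety Monitoring Board, the board receives the adverse event details and makes the final adjudication, so it would inherit the same gap.

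**Working it through.** The protocol gives no detection rate for this event, so there is no figure to reproduce.

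**Inputs from the protocol.** Event threshold: more than 5 minutes below 32°C. Recording interval T: 60 to 120 minutes. Planned hypothermia arm: 10 patients (Target Enrollment and Study Duration).

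**Assumptions.** The event is identified only from the charted readings. An excursion starts at a random time relative to them. Excursion length d is not given in the documents, so a range is shown.

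**Step 1: interval against threshold.** 60/5 = 12 and 120/5 = 24, so the gap between readings is 12 to 24 times the threshold.

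**Step 2: chance that at least one reading falls inside the excursion** = min(1, d/T).

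| Excursion length d | Hourly (d/60) | Two-hourly (d/120) |
|---|---|---|
| just over 5 min | 8.3% | 4.2% |
| 15 min | 25% | 12.5% |
| 30 min | 50% | 25% |
| 60 min | 100% | 50% |
| 90 min | 100% | 75% |
| 120 min | 100% | 100% |

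A simulation with 200,000 random start times gives 50.1% and 25.2% for the 30-minute row.

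**Step 3: confirming duration.** One low reading is compatible with a dip of any length, including one under 5 minutes. Two consecutive scheduled readings can both be low only if d exceeds T, that is, more than 60 minutes (hourly) or 120 minutes (two-hourly). For shorter excursions, an unscheduled recheck or another source is needed to show that 5 minutes were exceeded. The protocol specifies neither.

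**Step 4: what a zero count would mean.** Suppose, purely for illustration, that each of 10 cooled patients had one 10-minute excursion. The chance that none coincides with a reading is (1 - 10/60)^10 = 16% with hourly readings and (1 - 10/120)^10 = 42% with two-hourly readings. The expected number flagged is 10 × 10/60 = 1.7 or 10 × 10/120 = 0.8, although all 10 patients had a qualifying event.

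**Step 5: effect of finer capture.** With readings every s minutes and s no more than 5, min(1, d/s) = 1 for every d above 5, so every qualifying excursion contains a reading. The time from the first to the last low reading lies between d - 2s and d. It understates the duration by at most 10 minutes when s = 5 and by at most 2 minutes when s = 1.

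**The case against.** The strongest reply is that the protocol never says the event comes only from the 1-2 hourly entries. That sentence sets routine charting for both arms under a unit policy, and the statements about the adverse event and time in window are separate. The patient has an indwelling core probe and a console that measures temperature for feedback control, with nurses and physicians at the bedside. Unit protocols that are not part of the documents may already cover alarms or console logs. Staff who saw a value below 32°C would very likely look again well before the next scheduled entry.

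Most of this stands, and it rules out several stronger readings:

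- A reader might infer that temperature is measured only every 1-2 hours, or that undercounting is certain. The documents do not support this. They show that the source for the event is not named and that the one specified record is too coarse for it.
- A reader might infer that duration could never be confirmed for excursions under an hour. That holds only if nobody rechecks a low value. A recheck, however, starts only after a low reading has been seen, so it does not recover excursions that fall between readings.
- A reader might treat two silences as proof that no finer record is kept: the list under C. Monitoring of Safety ("24-hour monitored telemetry, with measurement of heart rate, blood pressure, oxygen saturation, and respiratory rate") omits temperature, and Appendix 1 has no cooling-arm temperature row. Neither proves it. The list is introduced as non-exhaustive, and the cooling-period rule is stated elsewhere.
- A reader might extend the criticism to time in the therapeutic window. Regularly spaced readings estimate that quantity with almost no average bias, so no defect of that kind is shown.

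**Conclusion.** The point holds, at low severity. As written, the recording rule cannot reliably support the event the protocol defines, and no section designates a record that could. If the charted readings are the source, 50% (hourly) to 75% (two-hourly) of 30-minute excursions would be missed, and 75% to 87.5% of 15-minute ones. A low or zero count would then be weak evidence of good temperature control.

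This rests on random timing of excursions and on no other source being used. The number of missed events cannot be stated, because the documents give no excursion rate.

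Nor should the point be read as a threat to the main comparison. No primary or secondary endpoint uses temperature. Arrhythmia, bleeding and hypokalemia are captured separately as primary safety endpoints. Excursions at least as long as the charting interval would be seen. The consequence is limited to safety reporting and what the DSMB can adjudicate.

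**What to change.** Name the data source in the temperature paragraph of Mitigating Risks associated with TH, with matching lines in C. Timing of Data Collection and Appendix 1.

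1. For the hypothermia arm, identify the below-32°C event from the thermal regulation system's record at intervals of 5 minutes or less, preferably 1 minute so that duration is well determined.
2. If that record cannot be exported, set a low-temperature alarm at 32°C and log the start and stop time of each alarm.
3. Keep 1-2 hourly charting for routine vital signs and for the control arm.

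The documents do not say whether the console can export or alarm, so confirm this before choosing. If neither is possible, the last resort is to redefine the event as any charted value below 32°C. That aligns the definition with the record but detects no more excursions, and it would also count a dip of under 5 minutes that happened to coincide with a reading.

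The cost is one or two sentences of text, plus one file for each of about 10 patients or one entry per alarm. The reported event count may rise. Sample size, arms and endpoints do not change.
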